8.9.2. COVID-19 Case Definitions

The incidence of COVID-19 will be assessed as an exploratory objective in Part 2 of this study. Active surveillance for COVID-19 and SARS-CoV-2 infection will be performed in both parts of the study (see Table 5 and Table 6).

To be considered as a case of COVID-19, the following case definition must be met:

- The participant must have at least 1 nasal swab (or respiratory sample, if hospitalized) positive for SARS-CoV-2 by RT-PCR AND
- ONE of the following:
 - Fever (temperature $\geq 38^{\circ}\text{C}/\geq 100.4^{\circ}\text{F}$) or chills (of any duration, including ≤ 4 hours)
 - Shortness of breath or difficulty breathing (of any duration, including ≤ 48 hours)
 - Cough (of any duration, including ≤ 48 hours)
 - Fatigue
 - Muscle or body aches
 - Headache
 - New loss of taste or smell
 - Sore throat
 - Congestion or runny nose
 - Abdominal pain
 - Nausea or vomiting

Protocol: mRNA-1273-P206, Original

- Diarrhea
- Poor appetite/poor feeding

Severe COVID-19:

To be considered severe COVID-19, the following criteria must be met:

- Confirmed COVID-19 as per the COVID-19 case definition, plus any of the following:
 - Meeting criteria for systemic inflammatory response syndrome based on age-specific variables (Table 5) OR
 - Respiratory failure or acute respiratory distress syndrome (defined as needing high-flow oxygen, noninvasive or mechanical ventilation, or extracorporeal membrane oxygenation), medical intervention for shock (intravenous fluids, vasopressors, etc.), OR
 - Significant acute renal, hepatic, or neurologic dysfunction (Table 6), OR
 - Admission to an ICU or death.

Table 5: Age-specific Cutoffs for Vital Signs and Laboratory Variables

	Heart Rate, Beats/Min		Respiratory	Leukocyte Count,	Systolic Blood
Age Group	Tachycardia	Bradycardia	Rate, Breaths/Min	Leukocytes × 10 ³ /mm ³	Pressure, mm Hg
1 month to 1 year	> 180	< 90	> 34	> 17.5 or < 5	< 70
> 1 year to 5 years	> 140	NA	> 22	> 15.5 or < 6	< 70 + (age in years × 2)

Abbreviations: AHA = American Heart Association; NA = not applicable.

Note: Lower values for heart rate or leukocyte count are for the fifth percentile and upper values for heart rate, respiratory rate, or leukocyte count are for the 95th percentile for the age group. Systolic blood pressure values are based on AHA definitions of hypotensive shock for pediatric population.

Source: Goldstein et al 2005 and Topjian et al 2020.

Protocol: mRNA-1273-P206, Original

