8.9.3. Surveillance for COVID-19 Symptoms

Surveillance for COVID-19 symptoms will be conducted via biweekly telephone calls or eDiary prompts as specified in Section 8.10.2 and Figure 2; starting after participant enrollment and continuing throughout the study.

[figure not shown]
If there is no response to an eDiary prompt for 2 days, the study site staff will contact the study participant by telephone.

According to the CDC, as of 22 Dec 2020 (CDC 2020a), patients with COVID-19 have reported a wide range of symptoms ranging from mild symptoms to severe illness. Throughout the study, to survey for COVID-19, the following pre-specified symptoms that meet the criteria for suspicion of COVID-19 will be elicited periodically (Section 8.10.2 and Section 8.9.4) from the participant, and the presence of any one of these symptoms (in the absence of an alternative diagnosis) lasting at least 48 hours (except for fever and/or respiratory symptoms) will result in the study site staff arranging an illness visit to collect a nasal swab for SARS-CoV-2 within 72 hours, or as soon as possible thereafter.

- Fever (temperature $\geq 38^{\circ}\text{C}/\geq 100.4^{\circ}\text{F}$) or chills (of any duration, including ≤ 48 hours)
- Shortness of breath or difficulty breathing (of any duration, including ≤ 48 hours)
- Cough (of any duration, including ≤ 48 hours)
- Fatigue
- Muscle or body aches
- Headache
- New loss of taste or smell
- Sore throat
- Congestion or runny nose
- Abdominal pain
- Nausea or vomiting
- Diarrhea
- Poor appetite/poor feeding

Protocol: mRNA-1273-P206, Original

Figure 2: Surveillance for COVID-19 Symptoms and the Corresponding Clinical Data Pathways

Abbreviations: COVID-19 = coronavirus disease 2019; HCP = healthcare practitioner; PCR = polymerase chain reaction; RT-PCR = reverse transcriptase polymerase chain reaction; SARS-CoV-2 = severe acute respiratory syndrome coronavirus 2.

Note: Blood sample for SARS-CoV-2 surveillance not shown in figure.

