It is important to note that some of the symptoms of COVID-19 overlap with solicited systemic ARs that are expected after vaccination with mRNA-1273.214 (eg, myalgia, headache, fever, and chills). During the first 7 days after vaccination, when these solicited ARs are common, investigators should use their clinical judgment to decide if a nasal swab should be collected. The collection of a nasal swab prior to the first dose on Day 1, prior to the second dose on Day 57, and then at all subsequent study visits (Day 85, Day 237, and Day 422) can help ensure that cases of COVID-19 are not overlooked. Any study participant who reports respiratory symptoms

Protocol: mRNA-1273-P206, Original

during the 7-day period after vaccination without an alternative diagnosis should be evaluated for COVID-19.

For children with febrile illnesses, if an alternative diagnosis is identified (eg, positive urine culture, streptococcal pharyngitis, cellulitis), the investigator may decide to omit the illness visit. Identification of an alternative viral agent (such as respiratory syncytial virus or influenza by rapid testing) does not satisfy this requirement, as co-infections with SARS-CoV-2 may occur.

An investigator may elect to omit the illness visit if standard-of-care testing prior to the illness visit reveals a negative COVID-19 NAAT performed at a CLIA-certified or CLIA-waived laboratory (or a laboratory of equivalent accreditation if the test was done outside the US) and the principal investigator can obtain a copy of the negative test. Home testing kits cannot be used to satisfy this testing requirement. Standard-of-care evaluation of household contacts that reveals a negative COVID-19 is not sufficient to omit an illness visit in the study participant.

During the course of the study, participants with symptoms of COVID-19 will be asked to return within 72 hours or as soon as possible to the study site or trained staff from the study site will conduct a home visit as soon as possible to collect a nasal swab sample (for RT-PCR) for evaluation of COVID-19. Both study site visits and home visits are referred to as illness visits (Section 8.9.3.1).

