Cases are defined as participants meeting clinical criteria based both on symptoms for COVID-19 and on RT-PCR detection of SARS-CoV-2 from samples collected within 72 hours of the study participant reporting symptoms meeting the definition of COVID-19. Participants who are hospitalized for COVID-19 without the opportunity for a clinic or home visit will also be considered cases, assuming that the symptomology criteria for COVID-19 are met and a respiratory sample is positive for SARS-CoV-2 by RT-PCR at a certified laboratory.

Investigators are encouraged to try to obtain a respiratory sample during the course of hospitalization or immediately after hospital discharge as an unscheduled visit for submission to the study central laboratory, if feasible. The investigator should determine if the criteria for severe COVID-19 have been met.

Severe COVID-19 is defined in Section 8.9.2.

All clinical findings will be recorded in the eCRF. All confirmed cases of symptomatic COVID-19 will be captured as MAAEs if an illness visit was conducted at the site or if they were evaluated by a healthcare provider, along with relevant concomitant medications and details about severity, seriousness, and outcome, and will be collected throughout the study period (Section 8.11.4).

Protocol: mRNA-1273-P206, Original

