6.5.1. Endpoint Definition/Derivation

6.5.1.1. CDC Case Definition of COVID-19

The incidence of the first occurrence of COVID-19 postbaseline, where COVID-19 is defined as symptomatic disease based on CDC case definition, starting 14 days after each injection of mRNA-1273.214, will be summarized using incidence rate (number of cases divided by the total person-time).

Cases are defined as participants meeting clinical criteria based on both symptoms for COVID-19 and positive RT-PCR test results.

A positive PCR result of the eligible symptoms are summarized below in Table 1.

Table 1 Derivation for CDC Case Definition of COVID-19

	COVID-19
Postbaseline PCR results	Positive, AND
Systemic Symptoms	at least ONE of the following systemic symptoms: Fever (temperature $\geq 38^{\circ}$ C/ $\geq 100.4^{\circ}$ F) or chills (of any duration, including ≤ 48 hours), fatigue, headache, myalgia, nasal congestion or rhinorrhea, new loss of taste or smell, sore throat, abdominal pain, diarrhea, nausea/vomiting, poor appetite/poor feeding; OR
Respiratory symptoms	at least ONE of the following respiratory signs/symptoms: cough (of any duration, including ≤ 48 hours), shortness of breath or difficulty breathing (of any duration, including ≤ 48 hours).

The date of documented CDC Case Definition of COVID-19 (case) will be the later date of ([systemic symptom reported, or respiratory symptom reported] and, [date of positive PCR test]). Specifically, the date of documented CDC Case Definition of COVID-19 will be the

later date of the following two dates (date of positive PCR test, and the date of eligible symptom(s)), and the two dates should be within 14 days of each other.

- Date of positive PCR test,
- Date of eligible symptom(s), defined as earliest of
 - Respiratory symptom: earliest date of an eligible respiratory symptom is reported
 - Systemic symptoms: earliest date of the eligible systemic symptom is reported

The time to the first occurrence of CDC Case Definition of COVID-19 will be calculated as:

Time to the first occurrence of CDC Case Definition of COVID-19 = Date of documented CDC Case Definition of COVID-19 – Date of Randomization + 1.

COVID-19 will be assessed primarily for cases starting 14 days after second injection, i.e. date of documented COVID-19 – Date of the 2^{nd} injection \geq 14. COVID-19 may also be assessed for cases starting after first injection, 14 days after first injection, and starting after second injection.

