6.5.3. Sensitivity and Subgroup Analysis

Sensitivity analysis for key efficacy endpoints will be performed with the same methods described above based on the mITT Set and mITT-1 Set, with cases counted starting from randomization in Part 2. A sensitivity analysis will be performed based on a modified version of the endpoint definition, including COVID-19 non-RT-PCR tests.

Subgroup analysis may be done for the following subgroups:

- Sex (male, female)
- SARS-CoV-2 status at baseline
- Maternal COVID-19 vaccine status
- Maternal COVID-19 infection status
- Breastfeeding history
- Race
- Ethnicity

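### The SAP's 14-day symptom-to-PCR pairing, with no rule for post-injection fever or poor feeding, can relabel asymptomatic infection as COVID-19, mainly outside the primary count

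*SAP*

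**What the plan says.** SAP 6.5.1.1 needs a positive postbaseline PCR and at least one systemic or respiratory symptom from Table 1, "and the two dates should be within 14 days of each other". The order does not matter, and scheduled swabs are not excluded. The case date is the later of the two dates. On the counting window it says "COVID-19 will be assessed primarily for cases starting 14 days after second injection", and it allows further counts starting after injection 1, 14 days after injection 1, and after injection 2. SAP 6.5.3 adds mITT and mITT-1 sensitivity analyses "with cases counted starting from randomization in Part 2". SAP 6.5.1.3 defines asymptomatic infection by no symptoms within 14 days either side of a positive test.

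The protocol is not uniform. Section 8.9.3 defines cases by symptoms and "RT-PCR detection of SARS-CoV-2 from samples collected within 72 hours of the study participant reporting symptoms meeting the definition of COVID-19", with a separate route for hospitalized infants. The same section tells sites "to collect a nasal swab for SARS-CoV-2 within 72 hours, or as soon as possible thereafter". Section 8.9.2 opens its definition with "The participant must have at least 1 nasal swab (or respiratory sample, if hospitalized) positive for SARS-CoV-2 by RT-PCR AND" and then asks for one listed symptom, with no interval.

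On reactions, protocol 8.9.3 warns that "some of the symptoms of COVID-19 overlap with solicited systemic ARs that are expected after vaccination with mRNA-1273.214" and leaves the decision to swab in the first 7 days to the investigator. Fever and loss of appetite appear among the solicited reactions (protocol Table 7, SAP 6.3.2) and in the COVID-19 symptom list. Neither document has an analysis rule for them.

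SAP Section 1 gives the SAP precedence over the protocol. SAP Section 7 lists only the Part 1 Arm 2 enrollment change.

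**The concern.** The SAP's window is wider than the only explicit timing rule for a case in the protocol, and it governs without being declared. Its practical effect comes through scheduled swabs. Investigator judgment about swabbing cannot help there, because those swabs are taken whether or not the infant has symptoms.

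The Day 57 swab is the clearest example. It is taken just before injection 2, so the solicited-reaction week follows at once. A silent positive on Day 57 with a reaction fever on Day 58 becomes a COVID-19 case dated Day 58, and the infant drops out of the asymptomatic count. A reaction fever on Day 58 with a silent positive on Day 71 or 72, at the early limit of the Day 85 visit, becomes a case in the primary window because the later date sets the case date.

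If fever or poor feeding is commoner after vaccine than after placebo, this misclassification differs by arm. It adds COVID-19 cases to the vaccine arm and removes asymptomatic infections from it.

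**Working it through.** The documents give no event count or power for this endpoint, so there is no figure of the plan's own to reproduce. Let day 0 be the day of injection 2 (nominal Day 57).

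1. **Inputs from the documents.** Solicited period: days 0 to 6. Pairing: 14 days or less apart, either order. Primary count: later date on day 14 or after. Day 85 visit window of -14/+7: 28 - 14 = day 14 to 28 + 7 = day 35, which is 22 days. Arm size: 300.

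2. **Which pairs reach the primary count.** A reaction on day s (0 to 6) pairs with a PCR on day p if p is at least 14 and p - s is at most 14. That allows s + 1 values of p, so 1 + 2 + ... + 7 = 28 pairs, all with p on days 14 to 20. These are the first 7 of the 22 allowed days for the Day 85 swab. A swab on its target day (day 28) cannot pair.

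3. **The same under 72 hours.** The latest PCR that can pair is on day 6 + 3 = 9, before day 14, so there are 0 pairs. This takes onset and report as the same day, which is reasonable for reactions because the eDiary is completed daily.

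4. **Size in the primary count.** Assumed: 10% to 30% of infants swabbed on days 14 to 20; PCR positivity 1% to 5%; fever or poor feeding after injection 2 in 20% to 60%. With reaction and swab days spread evenly, 28 of 7 × 7 = 49 combinations qualify (0.571).
   - Low: 300 × 0.10 × 0.01 × 0.20 × 0.571 = 0.03.
   - High: 300 × 0.30 × 0.05 × 0.60 × 0.571 = 1.5.

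5. **Size in the earlier-start and from-randomization counts.** A positive pre-dose Day 57 swab pairs with any reaction on days 0 to 6.
   - Low: 300 × 0.01 × 0.20 = 0.6.
   - High: 300 × 0.05 × 0.60 = 9.

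6. **Difference between arms.** Steps 4 and 5 give totals for one arm; placebo infants also have fever and poor feeding. If these are 15 points commoner on vaccine (assumed), the excess through the Day 57 swab is 300 × 0.01 × 0.15 = 0.45 to 300 × 0.05 × 0.15 = 2.25 infants. In the primary count it is 300 × 0.10 × 0.01 × 0.15 × 0.571 = 0.03 to 300 × 0.30 × 0.05 × 0.15 × 0.571 = 0.4.

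7. **Unrelated illness, both arms.** The chance that an unrelated illness starts within a span of d days is 1 - exp(-r × d/365). With r = 4, 6 and 8 illnesses a year (assumed):
   - SAP span, 29 days: 27%, 38%, 47%.
   - Swab 0 to 3 days after onset, 4 days: 4%, 6%, 8%.
   - Swab within 72 hours of a report made up to 14 days after onset, 18 days: 18%, 26%, 33%.

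**The case against.** The case against is substantial, and most of it stands.

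- A reader might infer that vaccine reactions themselves become COVID-19 cases. They do not: SAP Table 1 requires a positive RT-PCR (one sensitivity analysis in 6.5.3 also admits other tests). The error is to call a real infection symptomatic, and the total infection endpoint in 6.5.1.2 does not change.
- A reader might infer that the protocol has a single 72-hour rule which the SAP breaks. Section 8.9.2 states no interval, and 8.9.3 lets the swab come later than 72 hours. The missing reaction rule is also common to both documents, so it is not a SAP departure.
- A reader might set 38% against 6% and conclude that the SAP's window relabels about one in three silent positives. The protocol's 72 hours run from the report, not from onset, and scheduled contacts are about two weeks apart, later about four. With a lag of up to 14 days the contrast at 6 illnesses a year is 38% against 26%. The illness rate is assumed in any case.
- A reader might infer that the primary count is badly affected. Starting 14 days after injection 2 removes most of the overlap.
- Making 72 hours the main rule would open a gap. Under 6.5.1.3 as written, an infant with symptoms 4 to 14 days from a positive would be neither a COVID-19 case nor asymptomatic.
- The output is an incidence rate per arm with an exact interval; no vaccine efficacy test is planned. Protocol Section 9 lets exploratory changes be listed in the SAP or the study report, so silence in SAP Section 7 is not by itself a breach.

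What survives is that the two timing rules differ without explanation, and that scheduled swabs let solicited-period symptoms reclassify infections, probably unequally by arm.

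**Conclusion.** The point holds in limited form. The pairing rules in protocol 8.9.2, protocol 8.9.3 and SAP 6.5.1.1 do not agree, and the SAP does not declare its choice. With no rule for post-injection fever or poor appetite, an infected infant without COVID-19 symptoms can be moved into the COVID-19 count.

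The exposure is about 0.6 to 9 infants per 300 in the earlier-start and from-randomization counts, and about 0.03 to 1.5 in the primary count, through PCRs on days 14 to 20 only. The excess on vaccine would be smaller than either. Every rate behind these figures is assumed, since the documents give none for this product and age group. The expectation of more reactions on vaccine rests on the pattern in earlier mRNA-1273 studies (protocol 2.3.2); it would work against the vaccine.

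No primary or secondary hypothesis is touched. The endpoint is exploratory and descriptive, and it matters only if Part 2 is run, which the SAP still plans. The change is worth making because it is cheap and removes a misclassification that may differ by arm.

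**What to change.** 1. **SAP 6.5.1.1.** Fever or poor appetite/feeding that starts on the day of injection or the 6 following days should not qualify alone; another eligible listed symptom is needed. For the primary count, require symptom onset as well as the case date to be at least 14 days after injection 2. That removes all 28 pairs found above.
2. **SAP 6.5.1.3.** Use the same symptom rule, so that every PCR-positive infant is classed as exactly one of COVID-19 or asymptomatic infection. Classify first and apply the counting window afterwards.
3. **Pairing window.** Reconcile protocol 8.9.2, protocol 8.9.3 and SAP 6.5.1.1, and declare the chosen window with its reason in SAP Section 7. Report 72-hour pairing, keeping the route for hospitalized infants, as a sensitivity analysis and not as the main definition.

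The cost is SAP wording and one extra run of the case algorithm on data already collected. A few true cases whose only symptoms were fever or poor feeding in the week after injection leave the COVID-19 count. Cases with onset before day 14 but a PCR from day 14 on leave the primary count; those with another eligible symptom stay in the earlier-start counts. Both changes are best settled before unblinding.

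### SAP 6.5.1.1 does not tie the symptom date of a COVID-19 case to the illness in which the RT-PCR was positive, so a literal derivation can reject confirmed symptomatic cases

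*SAP*

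**What the plan says.** SAP 6.5.1.1 sets the case criterion: "Cases are defined as participants meeting clinical criteria based on both symptoms for COVID-19 and positive RT-PCR test results". The case is dated at the later of the positive PCR date and the eligible symptom date, with the condition that "the two dates should be within 14 days of each other".

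The symptom date is built in two layers. The outer layer reads "Date of eligible symptom(s), defined as earliest of", and the two items beneath it read "Respiratory symptom: earliest date of an eligible respiratory symptom is reported" and "Systemic symptoms: earliest date of the eligible systemic symptom is reported". Neither item says where the search for symptoms begins, how far back it goes, or that the symptom must belong to the illness that was swabbed. In Table 1 of that section, the postbaseline qualifier is attached to the PCR row only.

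The counting rule, "COVID-19 will be assessed primarily for cases starting 14 days after second injection", restricts the case date. It does not restrict the symptom search.

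Protocol 8.9.3 links symptom and swab more closely. It defines a case by "RT-PCR detection of SARS-CoV-2 from samples collected within 72 hours of the study participant reporting symptoms meeting the definition of COVID-19". SAP 6.5.1.3, on asymptomatic infection, looks for symptoms within 14 days either side of the positive test, so there the search is anchored on the test.

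**The concern.** Infants have many minor illnesses, and the eligible list includes runny nose, cough, fever, diarrhoea, vomiting and poor feeding. Protocol 8.9.3 says that "the following pre-specified symptoms that meet the criteria for suspicion of COVID-19 will be elicited periodically", from enrolment to the end of the study, so the data are likely to hold symptom dates from illnesses that were not COVID-19. A program that follows the SAP bullets in order would take the minimum of all those dates and then test the 14-day gap. One old cold could then disqualify a later confirmed case.

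Three consequences follow under that reading:

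- The COVID-19 incidence rate is biased downward, and more so late in follow-up, when there has been more time for an earlier symptom.
- Person-time in SAP 6.5.2 runs to the event, so a rejected case stays in the denominator.
- The infection falls between endpoints. It counts under 6.5.1.2 (infection regardless of symptoms). It is not a case under 6.5.1.1, and because symptoms lie within 14 days of the test, that test cannot count as asymptomatic under 6.5.1.3.

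The mITT and mITT-1 sensitivity analyses in SAP 6.5.3 use the same methods, so they would not reveal the problem.

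**Working it through.** The documents give no event count, symptom rate or power figure for this derivation, so there is no stated figure to reproduce. Two checks were made.

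**Check 1: do the two readings give different answers?**

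- Rule A (literal): symptom date = minimum of all eligible symptom dates; case if |PCR day − symptom day| ≤ 14.
- Rule B (anchored): symptom date = earliest eligible symptom within 14 days either side of the positive PCR; case if one exists.
- Under both, case date = later of symptom date and PCR date.

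| Symptom days | PCR day | Rule A | Rule B |
|---|---|---|---|
| 150 | 152 | case, Day 152 | case, Day 152 |
| 140, 150 | 152 | gap 12: case, Day 152 | case, Day 152 |
| 138, 150 | 152 | gap 14: case, Day 152 | case, Day 152 |
| 137, 150 | 152 | gap 15: not a case | case, Day 152 |
| 30, 150 | 152 | gap 152 − 30 = 122: not a case | case, Day 152 |
| 30 only | 152 | gap 122: not a case | not a case |

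The rules part only when the infant has a symptom near the PCR and also one more than 14 days before it. Rule A can then remove a case. It cannot add one, because if the overall minimum is inside the window, rule B finds the same date.

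**Check 2: how large could the loss be under rule A?**

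Assume that recorded eligible-symptom episodes follow a Poisson process with rate r per infant-year (an assumption; the documents give no rate) and that the search starts on Day 1. For a true case with PCR on day d, the disqualifying period is T = d − 15 days, and

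share lost = 1 − exp(−r × T / 365.25).

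The primary counting window opens at Day 57 + 14 = 71 and closes at Day 422; its middle is about Day 246. There T = 231:

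- r = 1: 1 − exp(−0.632) = 47%
- r = 2: 1 − exp(−1.265) = 72%
- r = 4: 1 − exp(−2.530) = 92%
- r = 6: 1 − exp(−3.795) = 98%

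The same formula at other days:

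| PCR day | T | r = 1 | r = 2 | r = 4 | r = 6 |
|---|---|---|---|---|---|
| 71 | 56 | 14% | 26% | 46% | 60% |
| 150 | 135 | 31% | 52% | 77% | 89% |
| 237 | 222 | 46% | 70% | 91% | 97% |
| 422 | 407 | 67% | 89% | 99% | about 100% |

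Under rule B the loss is 0% throughout.

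**The case against.** The best reply is that the bullets describe one documented case. On that view the 14-day condition belongs to the pair of dates that forms the case, and earliest means the first symptom of the illness paired with that PCR. The protocol's 72-hour sampling rule and the test-anchored search in SAP 6.5.1.3 both fit this, and the literal reading leaves an infection in neither the symptomatic nor the asymptomatic class, which is unlikely to have been intended. This reading is plausible and probably what was meant. But 6.5.1.1 does not state it, and the protocol cannot be assumed to supply it: the SAP uses 14 days rather than 72 hours, and its introduction says the SAP prevails where methods differ.

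The reply also limits the point, in three ways.

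- A reader might infer that the SAP prescribes the earliest symptom over all follow-up. It does not say so; that is one reading of silent text.
- A reader might infer that any infant with an earlier unrelated illness fails. Even read literally, an earlier symptom within 14 days of the PCR does no harm.
- A reader might take the percentages above as an expected loss. They rest on assumed rates and on every episode entering the derivation as a dated eligible symptom. The documents do not say that it would. Under protocol 8.9.3, an illness visit is triggered only without an alternative diagnosis and, fever and respiratory symptoms apart, only after at least 48 hours.

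**Conclusion.** The point holds as a gap in a stated derivation. SAP 6.5.1.1 admits two readings that give different case counts, and the literal one rejects confirmed symptomatic cases whose earliest eligible symptom is more than 14 days before the positive PCR. The size cannot be fixed from the documents: it is 0% under the same-illness reading and, at Day 246, about 47% to 98% under the literal reading with assumed rates of 1 to 6 episodes per year.

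The reach is narrow. COVID-19 incidence is an exploratory Part 2 endpoint outside the ten hypotheses. Primary immunogenicity and safety are untouched, and the infections still count under SAP 6.5.1.2. SAP Section 7 records an enrolment pause during Part 1, so the matter bites only if Part 2 is run; the SAP keeps these analyses in place.

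A reader might also infer a bias between arms, since protocol 8.9.3 notes that solicited reactions overlap with COVID-19 symptoms, so that early vaccine reactions could disqualify later vaccine-arm cases. The documents do not say whether solicited reactions enter the symptom data used here, so that conclusion is not supported.

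**What to change.** Replace the symptom-date bullets in SAP 6.5.1.1 with a rule of this kind:

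> For each positive postbaseline RT-PCR, the symptom date is the earliest eligible respiratory or systemic symptom dated no more than 14 days before or after that test. Each positive RT-PCR is assessed separately, and the first one with such a symptom defines the case.

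This matches the test-anchored search in SAP 6.5.1.3. The section should also say how the 14-day pairing relates to the 72-hour sampling condition in protocol 8.9.3, so that the two case definitions are reconciled. The cost is one or two sentences in the SAP and a line in the derivation program, with no new data. It should be settled before Part 2 data are unblinded.
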